5.2 Study Visits

5.2.1 Procedures for Screening and Enrolment (Visit 1; up to -5 weeks)

A signed and dated informed consent form will be obtained before screening procedures. Evaluations obtained as part of routine medical care and performed during the screening period may be used in place of the study specific evaluations. Subjects will acknowledge and agree to the possible use of this information for the study by giving informed consent.

After informed consent is obtained, subjects who are screened will be allocated a subject number. All screened subjects must be identifiable throughout the study. The investigator will maintain a list of subject numbers and names to enable records to be found at a later date if required.

Rescreening will not be permitted in this study.

The screening visit (Visit 1) will take place up to 5 weeks prior to the first dose of IMP being administered. The following assessments will be performed at screening:

- Demographic data (date of birth, sex, ethnicity, and race)
- Significant medical or surgical history, including ongoing medical conditions, AEs, gynaecological history, date of last menses
- Eligibility check (inclusion/exclusion criteria)
- Physical examination (including subject height and body weight)
- Pelvic examination
- Vital signs (sitting blood pressure and heart rate)
- Laboratory safety tests (blood sampling for biochemistry, haematology and urinalysis)

- Urine pregnancy test, method of contraception
- 12-lead ECG
- Pelvic type-B ultrasound scan (a result obtained within 1 month of the screening visit will be acceptable)
- Prior and concomitant medications/therapies (including medications and therapies for endometriosis)
- Record date of onset of last menses and expected date of onset of next menses

Each investigator will also maintain a record of all subjects screened into the study (i.e. who signed the informed consent form). Records up to the time of premature subject termination should be completed and the primary reason for termination will be recorded.

5.2.2 Procedures before Study Treatment (Baseline, Visit 2 Predose)

Subjects will be instructed to contact the study centre by telephone at the onset of their menses period to arrange their baseline visit (Visit 2, Day 1), which must occur in the follicular phase (from the first to the fifth day of menses). Administration of study treatment will be initiated at the baseline visit, following randomisation to one of the two treatment groups, as specified in Section 6.1. The following procedures will be performed at baseline on Day 1 of the study, prior to administration of study treatment:

- Urine pregnancy test
- Baseline efficacy assessments (E₂, LH and FSH concentrations; VAS)
- Samples taken for sparse PK analysis
- Vital signs
- Review of pretreatment AEs
- Prior and concomitant medications/therapies
- Date of onset of menses, current menses status
- Eligibility check (inclusion/exclusion criteria)
- Randomisation
- Allocation to the full PK/PD subgroup (selected sites only)

5.2.2.1 Pharmacokinetic Blood Sampling

Predose samples, as described in Section 5.2.2, will be the same for the full PK/PD subgroup and the sparse PK analysis. No additional predose samples are planned.

5.2.3 Procedures during Study Treatment (Visit 2 Postdose to Visit 8)

Subjects receiving triptorelin acetate PR 1-month will receive study drug at each visit during the treatment period up to and including Visit 7 (Week 20, Day 141±3). Subjects receiving triptorelin pamoate PR 3-month will receive study drug at Visit 2 (Day 1) and Visit 5 (Week 12, Day 85±3) only.

The following procedures will be performed on all subjects at Visit 3 (Week 4, Day 29±3) and Visit 4 (Week 8, Day 57±3):

- Efficacy assessments (E₂, LH and FSH concentrations (samples taken predose for subjects receiving triptorelin acetate PR 1-month); VAS)
- Samples taken for sparse PK analysis (samples taken predose for subjects receiving triptorelin acetate PR 1-month)
- Vital signs
- Review of AEs

- New or changed concomitant medications/therapies
- Review of menses status and record date of menses onset (if applicable)
- Injection of IMP (subjects receiving triptorelin acetate PR 1-month only)

The following procedures will be performed at Visit 5 (Week 12, Day 85±3):

- Efficacy assessments (E₂, LH and FSH concentrations (samples taken predose for all subjects); VAS)
- Samples taken for sparse PK analysis (samples taken predose for all subjects)
- Physical examination
- Pelvic examination
- Vital signs
- Laboratory safety tests (blood sampling for biochemistry, haematology and urinalysis)
- 12-lead ECG
- Pelvic type B ultrasound scan (optional based on subject's disease condition, as judged by the investigator)
- Review of AEs
- New or changed concomitant medications, including details of any "add back" therapy
- Review of menses status and record date of menses onset (if applicable)
- Injection of IMP (all subjects)

The following procedures will be performed at Visit 6 (Week 16, Day 113±3) and Visit 7 (Week 20, Day 141±3):

- VAS assessment
- Vital signs
- Review of AEs
- New or changed concomitant medications/therapies, including details of any "add back" therapy
- Review of menses status and record date of menses onset (if applicable)
- Injection of IMP (subjects receiving triptorelin acetate PR 1-month only)

The following procedures will be performed at Visit 8 (Week 24, Day 169±3):

- Efficacy assessments (E₂, LH and FSH concentrations; VAS)
- Physical examination
- Pelvic examination
- Vital signs
- Laboratory safety tests (blood sampling for biochemistry, haematology and urinalysis)
- 12-lead ECG
- Pelvic type B ultrasound scan
- Samples taken for sparse PK analysis
- Review of AEs
- New or changed concomitant medications/therapies, including details of any "add back" therapy

- Review of menses status and record date of menses onset (if applicable)

5.2.3.1 *Full Pharmacokinetic Blood Sampling during Treatment*

Triptorelin Pamoate PR 3-month

The full PK/PD subgroup will include up to 16 subjects receiving triptorelin pamoate PR 3-month. These subjects will attend the study centre for additional PK blood sampling at the following timepoints during the treatment period:

- Visit 2, Day 1 (0.5, 1, 2, 4, 8 and 12 hours postdose)
- Week 1 (24, 48 and 168 hours postdose)
- Week 2 (Day 15)
- Week 3 (Day 22)
- Week 6 (Day 43)
- Visit 5, Week 12 (Day 85, corresponding to the second administration of triptorelin pamoate PR 3-month): 0.5, 1, 2, 4, 8 and 12 hours postdose
- Week 13 (24, 48 and 168 hours postdose)
- Week 14 (Day 99)
- Week 15 (Day 106)
- Visit 6, Week 16 (Day 113)
- Week 18 (Day 127)
- Visit 7, Week 20 (Day 141)

In addition, at each visit, changes to ongoing and new AEs and concomitant medications and therapies will be recorded. Note that these PK blood samples are in addition to those described in Section 5.2.3.

Triptorelin Acetate PR 1-month

The full PK/PD subgroup will include up to 16 subjects receiving triptorelin acetate PR 1-month. These subjects will attend the study centre for additional PK blood sampling at the following timepoints during the treatment period:

- Visit 2, Day 1 (0.5, 1, 2, 4, 8 and 12 hours postdose)
- Week 1 (24, 48 and 168 hours postdose)
- Week 2 (Day 15)
- Week 3 (Day 22)
- Week 10 (Day 71)

In addition, at each visit, changes to ongoing and new AEs and concomitant medications and therapies will be recorded. Note that these PK blood samples are in addition to those described in Section 5.2.3.

5.2.3.2 *Full Pharmacodynamic Assessments*

The full PK/PD subgroup will comprise up to 32 subjects (up to 16 subjects from each treatment group; to be enrolled at selected sites). All subjects in the full PK/PD subgroup (both treatment groups) will attend the study centre for additional PD efficacy assessments (E₂, LH and FSH concentrations) at the following timepoints during the treatment period:

- Week 1 (Day 8)
- Week 2 (Day 15)
- Week 3 (Day 22)

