7.7.1 Adverse Events

A treatment-emergent adverse event (TEAE) is defined as any AE that occurs or worsens on or after the first dose of IMP, through 112 days (16 weeks) after last injection for triptorelin pamoate PR 3-month groups or through 56 days (8 weeks) after injection for triptorelin acetate PR 1-month group. Non-TEAEs and TEAEs will be separately summarised in tables and all AEs will be presented in the listing with flag of TEAE status.

All adverse events (AEs) recorded on the eCRF will be coded to SOC and PT using the MedDRA dictionary (version number is the newest version used in Covance coding system at the time of analysis). A subject will be counted at most once within a SOC and PT in summary tables.

In the summary table of TEAEs, the numbers and percentages of subjects and events will be tabulated and presented by treatment groups and overall for the following categories:

- Any TEAEs
- TEAEs with maximum intensity (Severe, Moderate, Mild)
- Serious TEAEs
- Drug-related TEAEs
- Drug-related serious TEAEs
- TEAEs leading to drug withdrawal
- TEAEs leading to drug interruption
- Serious TEAEs leading to drug withdrawal
- Serious TEAEs leading to drug interruption
- TEAEs leading to death

The numbers and percentages of subjects and events will be also be separately summarised by SOC and PT (sorted alphabetically) for each treatment group and overall as the above AE categories. The TEAEs with intensity of Severe will be separately summarised by SOC and PT (sorted alphabetically) for each treatment group and overall. The TEAEs and drug-related TEAEs will be also separately summarised by maximum intensity, SOC and PT (sorted alphabetically) for each treatment group and overall.

TEAEs or drug-related TEAEs with PTs observed $\geq 5\%$ or $\geq 10\%$ of subjects in any one of the treatment groups will be separately summarised by SOC and PTs.

In the event of multiple events being reported by the same subject, the maximum intensity (severe, missing, moderate, mild) and the most serious causality (related, not related) will be chosen. If severity is missing for one event and the subject had no intensity of severe in the same category events, “missing” row should be added after severe in the summary tables with maximum intensity.

Statistical Analysis Plan

Version: Final 3.1

Ipsen Pharma; Protocol No. D-CN-52014-220

Date of Issue: 13DEC2019

CCI

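### After the Week 12 visit the 3-month PK/PD subgroup has 7 to 9 scheduled AE-recording visits to Week 24 and the 1-month subgroup has 3, and the TEAE tables pool these women by arm without a check

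*Protocol*

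**What the plan says.** **Visits for all women.** Protocol 5.2.3 schedules AE review at Weeks 4, 8 and 12. After Week 12 the visits are set out under "The following procedures will be performed at Visit 6 (Week 16, Day 113±3) and Visit 7 (Week 20, Day 141±3" and "The following procedures will be performed at Visit 8 (Week 24, Day 169±3", and AE review is listed at each.

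**Extra visits in the PK/PD subgroup.** Protocol 5.2.3.1 gives one list per arm. For the test arm, "The full PK/PD subgroup will include up to 16 subjects receiving triptorelin pamoate PR 3-month". Their list resumes after the second injection with "Week 13 (24, 48 and 168 hours postdose", then Weeks 14, 15 and 16, "Week 18 (Day 127" and Week 20. For the comparator, "The full PK/PD subgroup will include up to 16 subjects receiving triptorelin acetate PR 1-month", and their treatment-period list ends at Week 10. Both lists close with the same instruction: "In addition, at each visit, changes to ongoing and new AEs and concomitant medications and therapies will be recorded".

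**Tables.** In Protocol Tables 3 and 4, the AE row as it reads in the text available to me has one mark for the three Week 1 attendances and one for the three Week 13 attendances. The row is not split by arm.

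**Analysis.** SAP 7.7.1 states: "In the summary table of TEAEs, the numbers and percentages of subjects and events will be tabulated and presented by treatment groups and overall". The population is the Safety Set, and TEAEs count from the first dose. Protocol 10.4.8 also tabulates by treatment group and overall. Neither document plans an AE table by PK/PD subgroup membership or a repeat without that subgroup.

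**The concern.** Mild or short-lived events are more likely to be recorded when women are asked more often. After the Week 12 visit the extra asking takes place in the 3-month arm only. It includes contacts 24, 48 and 168 hours after the second 3-month injection. Women in the 1-month subgroup are injected at Weeks 12, 16 and 20, but their next scheduled AE review comes four weeks later each time.

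Part of any excess of TEAEs in the 3-month arm could therefore reflect the visit schedule and not the product. The safety profile of the 3-month formulation is a secondary objective, and SAP 7.7.1 tabulates events as well as subjects. Event counts are the more exposed of the two, because a subject counts at most once within a SOC and PT.

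**Working it through.** **1. Check the schedule against the plan's own figures.** Protocol Table 6 gives 29 additional PK samples per 3-month subgroup subject and 15 per 1-month subject. Counting the timepoints in 5.2.3.1 and 5.2.4.2:

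- 3-month: (6+3+1+1+1) to Week 6, plus (6+3+1+1+1+1+1) from Week 12 to Week 20, plus 3 in follow-up = 29.
- 1-month: (6+3+1+1+1) to Week 10, plus 3 in follow-up = 15.
- Blood volume: 47.5 + 29×2 + 4×4 = 121.5 mL, and 47.5 + 15×2 + 4×4 = 93.5 mL.

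All four figures match. The 15 samples leave no room for an extra 1-month PK visit between Weeks 12 and 24.

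**2. Count scheduled AE-recording visits per woman after Day 1.**

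| Window | 3-month subgroup | 1-month subgroup | Everyone else |
|---|---|---|---|
| To Week 12, prose | 9 (24, 48, 168 h; Weeks 2, 3, 4, 6, 8, 12) | 9 (24, 48, 168 h; Weeks 2, 3, 4, 8, 10, 12) | 3 |
| After Week 12 to Week 24, prose | 9 (24, 48, 168 h; Weeks 14, 15, 16, 18, 20, 24) | 3 (Weeks 16, 20, 24) | 3 |
| Total, prose | 18 | 12 | 6 |
| Total, one mark each for Weeks 1 and 13 | 7 + 7 = 14 | 7 + 3 = 10 | 6 |

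**3. Average over the arm, in the window the TEAE tables use.** Inputs: 150 women per arm (Protocol synopsis), 16 in each subgroup (the ceiling), all visits attended. Arm mean = (16 × subgroup visits + 134 × 6) / 150.

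- Prose: (16×18 + 804)/150 = 7.28 against (16×12 + 804)/150 = 6.64; ratio 1.10.
- Table reading: (16×14 + 804)/150 = 6.85 against (16×10 + 804)/150 = 6.43; ratio 1.07.
- With 8 women per subgroup (assumed), prose: (8×18 + 142×6)/150 = 6.64 against (8×12 + 142×6)/150 = 6.32; ratio 1.05.

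**4. Illustrate the effect on TEAE incidence.** The documents give no TEAE rate and no effect of asking more often, so both inputs are assumed: baseline p of 30% to 50%, and a relative rise r of 10% to 50% in the 16 women. Change in the arm percentage = (16/150) × p × r.

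- Low end: 0.1067 × 0.30 × 0.10 = 0.0032, or 0.3 points.
- High end: 0.1067 × 0.50 × 0.50 = 0.0267, or 2.7 points.
- Standard error of a difference between two arms of 150, √(2p(1−p)/150): 5.3 points at p = 0.30 and 5.8 at p = 0.50.

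**The case against.** The strongest reply is that this is too small to matter. It involves at most 16 of 150 women per arm (10.7%), and the other 134 have identical treatment-period schedules. Protocol 8.1.3 frames the AE question around the time since the last assessment, and spontaneous reports are also taken. The arms therefore differ in how often women are asked, not in the time covered. The safety analysis is descriptive, and any bias runs against the test product, so it would not hide harm from the 3-month formulation. The listings would let a reader look into the matter without new tables. All of this stands, and it limits the importance. It does not remove the asymmetry, and no planned table shows whether it matters.

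Three stronger readings are tempting but not supported:

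- **An excess of 21% in contacts.** From the Week 12 visit alone the arm means are (16×9 + 134×3)/150 = 3.64 against 3.00. The TEAE tables count from first dose, however, and over that window to Week 24 the excess is about 7-10%.
- **Nine visits against three as settled.** The prose gives 9. Table 4 as it reads gives 7. The single mark may be a merged cell, so neither count is certain.
- **A large shift in incidence.** One could suppose that reporting in these 16 women rises from, say, 40% to 60-70%. Nothing in the documents supports such a jump. A woman who already has a TEAE by Week 12, when contacts are equal, cannot be added again to the any-TEAE row.

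**Conclusion.** The point holds as a minor one. The schedule makes AE questioning one-sided after the Week 12 visit, 9 or 7 scheduled visits against 3, in at most 16 women per arm, and the planned TEAE tables cannot show its effect. At arm level it amounts to about 7-10% more scheduled AE contacts to Week 24, assuming full subgroups of 16 and complete attendance, and less with smaller subgroups.

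The consequence for TEAE incidence is not derivable from the documents. The 0.3-2.7 point range is an illustration on assumed inputs, and all of it lies below the standard error of the difference. Mild or short-lived events and event counts are the most exposed. No hypothesis test or noninferiority conclusion is affected.

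**What to change.** In SAP 7.7.1, add a supplementary repeat of the TEAE overview and of the SOC/PT TEAE table (subjects and events) in the Safety Set excluding the full PK/PD subgroup. In those women, scheduled AE contacts are the same in both arms (6 each after Day 1 to Week 24). State alongside that AE contacts after the Week 12 visit differ by arm within the subgroup. Leave the main tables unchanged. The repeat should stay supplementary, because Protocol 5.2.2 lists allocation to the subgroup after randomisation in an open-label trial.

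Separately, reconcile the AE rows of Protocol Tables 3 and 4 with the prose of 5.2.3.1, so that it is clear whether AEs are recorded at each of the 24, 48 and 168 hour attendances.

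The cost is two extra tables and one sentence of text. The repeat has up to 32 fewer women, and it also leaves out their data before Week 12, when contact numbers in the two subgroups were equal.

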5.2.4 Procedures during Follow Up Period (Visit 9 to End of Study)

The purpose of the follow up period is to monitor menses recovery. Visits 9, 10 and 11 (Weeks 28, 32 and 36) will be conducted by telephone, primarily to establish if subjects' menses have recovered. If menses recover during the follow up period, subjects should attend the study site within 15 days after the first day of menses recovery. If there is no menses recovery by Week 40, the subject should attend the study site at Week 40 (Day 281±3). The first visit after menses recovery, or Week 40 (whichever is earlier) will be considered the end of study visit (see Section 5.2.4.4).

5.2.4.1 Follow Up Visits to be Conducted by Telephone

The following procedures will be performed by telephone at Visit 9 (Week 28, Day 197±3), Visit 10 (Week 32, Day 225±3) and Visit 11 (Week 36, Day 253±3) if required:

- Review of AEs
- New or changed concomitant medications/therapies
- Review of menses recovery status and record date of menses onset (if applicable)

5.2.4.2 Full Pharmacokinetic Blood Sampling during Follow Up

Subjects included in the full PK/PD subgroup will attend the study centre for PK blood sampling at the following timepoints during the follow up period:

- Visit 9, Week 28 (Day 197)
- Visit 10, Week 32 (Day 225)
- Visit 11, Week 36 (Day 253)

Note that subjects included in the full PK/PD subgroup will be required to attend full PK sampling visits during the follow up period, even if their menses recover prior to Week 40.

5.2.4.3 Full Pharmacodynamic Assessments during Follow Up

Subjects included in the full PK/PD subgroup will have an additional PD blood sample at Visit 10, Week 32 (Day 225).

Note that subjects included in the full PK/PD subgroup will be required to attend this PD sampling visit during the follow up period, even if their menses recover prior to Week 40.

5.2.4.4 End of Study Visit or Early Withdrawal Visit

The end of study visit will be the first visit within 15 days after the first day of menses recovery, or at Week 40 (Day 281±3), whichever is earlier. Subjects who withdraw from the study early will also attend an end of study visit.

Subjects who participate in the study in compliance with the protocol for 24 weeks of study drug administration will be considered to have completed study treatment. Subjects who participate in the study in compliance with the protocol for the 24 weeks of study drug administration, and complete the follow up period, will be considered to have completed the study.

For subjects who complete the study, or for those who withdraw prematurely from the study, final evaluations will be performed on the last day the subject receives the study drug, or as soon as possible afterwards. Subjects with ongoing AEs or clinically significant laboratory test abnormalities (as determined by the investigator) will be monitored as described in Section 8.1.3 and Section 8.1.2.4, respectively.

The following procedures will be performed at the end of study visit:

- E₂, LH and FSH concentrations (only if the subject's menses does not recover before Week 40)

- VAS assessment
- Vital signs
- Review of AEs
- New or changed concomitant medications/therapies
- Review of menses recovery status and record the date of menses onset (if applicable)

